Project title: Utilizing telemedicine for delivery of postoperative care following minimally-invasive gynecologic surgery: A randomized controlled trial

Principal Investigator: [name] MD FACOG

Co-Investigators: [name] MD

Research Associate: [name]

Biostatistician: [name]., Professor

Affiliations: Texas Tech University Health Science Center El Paso, Paul L. Foster School of Medicine

Background:

The wide-spread use of minimally invasive techniques in gynecologic surgery has brought several tangible benefits to patients including faster-recovery times, shorter hospital stays, decreased risk of long term complications, to name a few.¹⁻³ Technological advances such as the development of robotic assistance have allowed to further expand the number of cases that can be performed via a minimally invasive approach.⁴ The shift has been such that the landscape regarding operative routes in gynecologic surgery has completely reversed, with now the majority of cases being performed laparoscopically.⁵ Although much has changed intraoperatively, the surrounding structure of an operative has lagged. Specifically, preoperative and post-operative visits are still conducted in a similar way than how it was done 20 years ago. Despite leaps in technology, the field of gynecologic surgery has been slow to widely implement these advances into perioperative practice. One of the specific areas of opportunity is the postoperative visit. It is common practice in the majority of fields to have a visit with the patient approximately 2 weeks after surgery. The objective of this visit is to evaluate how the patient has been progressing, examine the wound site(s), and discuss pathology results from any specimens that were removed during the procedure.

The logistics of this visit involve blocking a time-slot in an established clinic day. Patient is required to transport herself to the clinic site. Once checked-in, there may be a waiting period before being placed in a room for the practitioner to conduct the visit. Once the visit is started, as long as there are no issues, the duration of the interaction may range on average between 3-7 minutes.

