Despite these visits being short and usually straight-forward, the invested time that patients have to dedicate is substantially greater than the actual interaction with the clinician. Furthermore, because of the advantages of minimally invasive surgery, many patients have already returned to work by the time of the postoperative visit which may result in a disruption of their daily work schedule.

The ubiquitousness of high-speed internet and mobile phones have allowed for the field of tele-medicine to thrive in recent years.^{6,7} Although wide-spread application of this modality has not been implemented in the field of gynecologic surgery, other areas such as urology and pediatrics have successfully implemented tele-medicine programs, specifically for postoperative patients, yielding promising results.^{8,9}

We propose a pilot project in which enrolled patients undergoing major gynecologic surgery will be randomized to either a traditional office postoperative visit or a telemedicine postoperative visit. The two groups will then be compared on a variety of metrics including clinical outcomes, patient satisfaction and time.

Objectives

1. Determine if there are differences in patient satisfaction between traditional postoperative visits and telemedicine postoperative visits
2. Determine the difference in time invested from the patient's side and clinicians side in order to complete the postoperative visit interaction
3. Analyze if there is a difference between groups regarding visits to the emergency department related to the surgery, delayed postoperative complications, etc.

Hypothesis

Patient satisfaction will be greater in the tele-medicine group.

Total time invested will be decreased.

There will be no difference in visits to the emergency department or unrecognized postoperative complications

Inclusion criteria

Female patients between ages 18-60

Have access to smart-phone with video /audio and internet capabilities

Undergoing laparoscopic gynecologic surgery that requires a postoperative visit

- Total laparoscopic hysterectomy
- Laparoscopic removal of adnexal structures
- Laparoscopic excision of endometriosis

Exclusion criteria

Patient unwilling to participate

Patient unwilling to install and utilize the telemedicine app on their smart phone.

Recruited participants will be deemed ineligible to continue the study if:

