- After recruitment, participant experiences surgical complications (bladder or bowel injury, etc) that require face-to-face postoperative care
- After recruitment, participant visits the emergency room (ER) for postoperative complaints between surgery and scheduled postoperative visit

Materials and Methods

Study design: Randomized controlled trial.

Once IRB approval is obtained, we will begin recruitment based on the stated inclusion and exclusion criteria. Invitation to participate will be extended to eligible patients by clinic staff with a direct care relationship to the patient during their pre-operative visit in the TTUHSC El Paso Ob-Gyn department. If the patient agrees to participate, research staff will be called in to explain the study in more detail. The patients will be advised that if they agree to enroll, there is a 50% chance their post-operative visit may be via tele-medicine and 50% chance it will be as a traditional visit in the office. They will be asked to fill out a short survey that verifies they have a compatible mobile phone, and will be asked to download the appropriate app. An instruction sheet on how to utilize the tele-medicine application will be given to all patients, to be used in case they are allocated to the tele-medicine group. Once enrolled, surgery will proceed as planned. After surgical stop-time, patients will be allocated to either a traditional postoperative visit group or a tele-medicine postoperative visit via block-randomization, utilizing block sizes of 4:6. This will be achieved by giving patients a sealed envelope that allocates them in a sequential fashion based on a previously generated random series. The envelope will contain information regarding group assignment, along with simple instructions as to how to schedule the post-operative visit within a window between one and three weeks from the surgery.

Both the tele-medicine and traditional visits will be carried out using the same structure.

- 1) Inquire about any concerns the patient has regarding recovery.
- 2) Review findings and procedures done during surgery and pathology results.
- 3) Visually examine abdominal laparoscopic port-sites.
- 4) The opportunity for the patient to ask any additional questions.

In the case of the telemedicine visits, they will open by asking the patient to state her full name, and her date of birth. Additionally, this will be correlated with the code in the instruction sheet in order to verify identity.

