A video-call application that is HIPAA compliant and easily accessible from mobile phones or video-enabled PCs will be used (doxy.me). A Business Associate Agreement between TTUHSC and Doxy.me has been generated in order to comply with HIPAA requirements. Patients will be given a time when they will receive their virtual appointment link, which will be sent to their mobile phone via text. It is expected that patients will use their phone to establish the connection. Providers will utilize a computer station set up with a camera and audio equipment, with a professional appearing backdrop. As part of the consent form, patients will be made aware that they may incur in data charges if they are using a limited data plan, and they are responsible for this expense.

Data will be collected in a de-identified manner. Baseline variables that will be captured include age, ethnicity, BMI, parity, distance from home address to the clinic in miles (calculated using Google maps). Surgery performed and operating time will also be collected. Post-operative visits will be timed. In the case of telemedicine, recorded time will be from when connection is established until disconnection. In the case of the traditional visit, it will be time from when the provider enters the exam room until time the patient exits). Patients will be contacted by phone between 7 to 14 days after the postoperative visit and they will be subjected to a PSQ-18 (Patient satisfaction questionnaire) focused on their post-operative visit, which will be conducted by a member of the research staff blinded to allocation. We will also inspect their medical records to determine if there were any phone calls to the clinic/call-center or visits to the emergency department following the postoperative encounter (within the first 30 days after surgery). In addition to the PSQ-18 questions (after they are completed), patient's will be asked "If they had the opportunity to have switched groups, would they?" and then they will be asked to give an estimate of how much time they utilized in order to complete the postoperative visit including transportation, waiting time, etc. (rounded to the nearest 15 minute increment).

Sample size:

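### Rounding total patient time to the nearest 15 minutes is too coarse for the telemedicine arm, where short totals may collapse to 0 or 15 minutes

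*Combined protocol and SAP*

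**What the plan says.** Objective 2 in the protocol is to "Determine the difference in time invested from the patient's side and clinicians side in order to complete the postoperative visit interaction", and the Hypothesis section expects total time to fall with telemedicine.

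The only measure of the patient's total time is in Materials and Methods. "Patients will be contacted by phone between 7 to 14 days after the postoperative visit", and after the PSQ-18 and a question about switching groups they are asked to "give an estimate of how much time they utilized in order to complete the postoperative visit including transportation, waiting time, etc". The answer is "rounded to the nearest 15 minute increment". The surveyor is blinded to allocation.

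The visit itself is timed separately. For telemedicine, "recorded time will be from when connection is established until disconnection"; for the office visit, "it will be time from when the provider enters the exam room until time the patient exits". Neither clock covers travel or waiting. No log or check-in time is described for the total.

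On length, the Background says of a straightforward office visit that "the duration of the interaction may range on average between 3-7 minutes". Materials and Methods adds that "Both the tele-medicine and traditional visits will be carried out using the same structure". The protocol gives no figure for a telemedicine patient's total time, and none for office travel and waiting beyond saying that they far exceed the contact itself.

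**The concern.** The recording unit is two to five times the length of the clinician contact as the Background describes it (15/7 = 2.1; 15/3 = 5). An office total that includes travel and waiting probably spans many 15-minute steps, so rounding does little to it. A telemedicine total may sit close to the 7.5-minute cut between 0 and 15. The same rule then treats the two arms differently in practice: one keeps its distribution, and the other may be reduced to one or two values.

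At stake is the size of the time saving, any percentage summary of it, and the spread in the telemedicine arm, on which a confidence interval or t-test depends. Precision lost at recording cannot be recovered later.

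**Working it through.** **Plan's own figure.** The plan gives no sample size, standard deviation (SD) or expected effect for patient time, so there is nothing to reproduce for this outcome. Its one calculation, 64 patients for satisfaction, is unaffected by this point.

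**Inputs from the protocol.** Rounding unit 15 minutes (Materials and Methods). Clinician contact 3-7 minutes (Background, for the office visit). The same visit structure in both arms (Materials and Methods), which is the basis for carrying 3-7 minutes over to the call.

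**Assumed inputs.** Call length V is uniform on 3-7 minutes. Telemedicine overhead H (waiting for the link, set-up) is uniform over several ranges. Office totals are normal with mean/SD 60/20, 90/30 and 120/40 minutes.

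**Rounding rule.** R(x) = 15 × floor(x/15 + 0.5). Totals under 7.5 give 0, totals from 7.5 to under 22.5 give 15, and totals from 22.5 to under 37.5 give 30. In whole minutes, 1-7 become 0 and 8-22 become 15.

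**Telemedicine arm.** The total is V + H.
- The true mean is 5 + mean(H).
- The true SD is sqrt[(4² + w²)/12], where w is the width of the range of H.
- For H uniform on 0 to h, with h at least 4.5, the share of zeros is the average of (7.5 - V)/h, which is 2.5/h.

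| Assumed overhead (min) | True mean | Recorded as 0 | Recorded mean | Mean error | True SD | Recorded SD |
|---|---|---|---|---|---|---|
| None | 5.0 | 100% | 0 | -5.0 | 1.2 | 0 |
| 0-5 | 7.5 | 2.5/5 = 50% | 7.5 | 0 | 1.85 | 7.5 |
| 0-10 | 10.0 | 2.5/10 = 25% | 0.75 × 15 = 11.25 | +1.25 | 3.1 | 6.5 |
| 5-15 | 15.0 | 0% | 15 | 0 | 3.1 | 0 |
| 0-20 | 15.0 | 2.5/20 = 12.5% | 15 | 0 | 5.9 | 7.5 |

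In the last row another 12.5% are recorded as 30, so the mean is 0.75 × 15 + 0.125 × 30 = 15. Simulation of 400,000 totals per row agrees with these values.

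The mean error has no fixed sign. The recorded SD is wrong in every row, too large in some and zero in others.

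**Office arm.** Simulated office totals have a mean rounding error of 0.03 minutes or less. The SD moves from 19.9 to 20.3, 29.9 to 30.2 and 39.9 to 40.1 minutes.

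**Effect on the arm difference.** Rounding moves any one value by at most 7.5 minutes, so each arm's mean moves by at most 7.5. With the office error near zero, the bias in the difference is at most about 7.5 minutes. For illustration, with assumed true savings of 60 and 30 minutes:
- No overhead: the saving is recorded as 65 instead of 60 (5/60 = 8% too large), or 35 instead of 30 (5/30 = 17% too large).
- Overhead 0-10: the saving is recorded as 58.75 instead of 60 (1.25/60 = 2% too small), or 28.75 instead of 30 (1.25/30 = 4% too small).
- As a percentage of office time, with no overhead and an office mean of 65: the true saving is 60/65 = 92%, recorded as 65/65 = 100%.

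**The case against.** The strongest reply is that the 15-minute unit and the 3-7 minute figure describe different things. The 3-7 minutes are clinician contact at an uncomplicated office visit. The rounded quantity is the patient's total, which for telemedicine also includes waiting for the texted link and connecting, while the call itself opens with an identity check. A zero needs the whole total to be under 7.5 minutes. This stands, and it is why no single share of zeros can be given.

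A reader might therefore infer too much in four ways:

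- **That telemedicine visits will generally be recorded as zero and the saving overstated.** The 100% zeros and the 8% and 17% inflation require no overhead for any patient. The other spreads tried give a mean error of nil, or slightly positive, which understates the saving.
- **That recall error differs by arm, or that the preceding questions colour the answer.** Both are plausible with unblinded patients, but the documents offer nothing from which to estimate either. The question order also puts the primary questionnaire first, which protects it.
- **That rounding adds material noise to the office arm.** The rounding SD is 15/sqrt(12) = 4.3 minutes, which hardly changes an SD of 20 or more.
- **That patient time should be moved to clock entries at the visit.** The return trip would have to be forecast, time could end up defined differently in each arm, and collection would pass from the blinded surveyor to staff who know the allocation. The documents describe no existing form for such entries.

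It is also fair to say that the timed call offers a check. With no overhead it equals the patient's total, so the worst case could be detected. With overhead it cannot restore the total.

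Finally, patient time is not the primary outcome, and the Background calls the study a pilot. Both are true and keep the point minor.

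**Conclusion.** The point holds as a minor one about precision. Total patient time is recorded only as a recalled estimate in 15-minute steps, and that step is coarse for the telemedicine arm. Over the overheads assumed, zeros run from 0% to 100%, the mean error from -5 to +1.25 minutes, and the recorded SD from 0 to 7.5 minutes against true values of 1.2 to 5.9.

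The bias in the arm difference is at most about 7.5 minutes. It would probably not reverse the direction if office travel and waiting are as long as the Background implies. It can distort the size or percentage of the saving and the spread in one arm.

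This rests on carrying the 3-7 minute figure over to the call, on the assumed overheads, and on office totals of about an hour or more. The documents do not support a claim that the saving will be overstated.

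**What to change.** In Materials and Methods, in the description of the follow-up call, delete the instruction that the answer be "rounded to the nearest 15 minute increment". Have the blinded surveyor record the patient's estimate in minutes, in the same call and with the same wording in both arms.

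The change needs no extra contact, leaves collection with the blinded surveyor, and costs essentially nothing. The small downside is that patients may still round their own recalled answers, so the gain is mainly for short telemedicine totals. It is a cheap improvement and not a condition for starting the trial.

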Our primary outcome is to detect a difference in patient satisfaction. If we expect a 20% relative increase in the experimental arm, assuming two-tailed testing with an alpha of 0.05, and power of 80%, we will need a total sample size of 64 patients. This is considering a base satisfaction score of 70, with a standard deviation of 20.

Safety Procedures:

-Confidentiality and Privacy: Data will be stored in a secure de-identified database. No personal/identifiable information will be collected in this database. A separate list that contains a list of enrolled patients, with information including patient name, phone number and internal research code will also be generated for the purpose of performing the follow-up surveys. The information from the surveys will then be uploaded into the de-identified database by using the internal research code.-Safety – A member of the research staff will be assigned as a safety monitor. Interval analysis will be performed for every 20 patients recruited. If the experimental arm demonstrates an increase of greater than 10% in visits to the emergency-room related to post-operative complaints, or an increase in unexpected complications (wound infection, wound dehiscence, etc.), the study will be halted. However, only patient's undergoing minimally invasive surgery will be included, which is known to have a lower wound-related complication rate than traditional surgery, so we do not expect any significant difference regarding complications.

Data Management:

All data will be collected in a de-identified fashion and stored on Redcap, which is approved TTUHSC IT software. Only approved members of the research team will be granted access. The data will be stored in a secured server. Data will not be linked by code to any identifying information.

Data analysis:

All data analysis will be carried out in SPSS version 24 (IBM, Armonk, NY, USA). We will use T-student to compare demographic variables that are continuous (age, BMI), as well as duration of the visit and number of readmissions or phone-calls. Pearson's Chi Square will be used when analyzing categorical binary variables.

Strengths/limitations

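### The emergency-room rule appears to drop randomised patients who know their arm from the satisfaction comparison, and 64 is not labelled as randomised or analysed

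*Combined protocol and SAP*

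**What the plan says.** The discontinuation list that follows Exclusion criteria opens with "Recruited participants will be deemed ineligible to continue the study if". Its second item is "After recruitment, participant visits the emergency room (ER) for postoperative complaints between surgery and scheduled postoperative visit".

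Materials and Methods fixes the order of events. Allocation comes at the end of surgery: "After surgical stop-time, patients will be allocated to either a traditional postoperative visit group or a tele-medicine postoperative visit". It is not concealed from the patient afterwards: "The envelope will contain information regarding group assignment". The visit is booked for one to three weeks after surgery. The primary outcome instrument, the PSQ-18, comes later still: "Patients will be contacted by phone between 7 to 14 days after the postoperative visit", with questions "focused on their post-operative visit".

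The Sample size section names satisfaction as the primary outcome and states a 20% relative increase, two-tailed alpha 0.05 and 80% power. It concludes "we will need a total sample size of 64 patients" and adds "This is considering a base satisfaction score of 70, with a standard deviation of 20". It does not say whether 64 is a number enrolled, randomised or analysed, and it gives no allowance for loss. Neither Data analysis nor any other section defines an analysis population, an analysis by assigned arm, a replacement rule or a method for missing scores.

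**The concern.** The emergency-room window opens at surgery, so the rule acts on patients who already hold an assignment, and it acts before their satisfaction is measured. A patient who cannot continue has no planned PSQ-18 score. If the rule is followed literally, the primary comparison is made among patients selected by something that happened after randomisation, and those patients knew their arm when it happened.

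Strengths/limitations rests the study's strength on randomisation and accepts that patients cannot be blinded. Selection after allocation weakens that protection. If removal differs between arms, and removed patients would have scored differently from those who stay, the difference in satisfaction is biased. Recruiting more patients would not cure this.

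A smaller matter goes with it. Satisfaction is the only outcome with a stated power. If 64 is the number randomised, each removed or unreached patient lowers that power.

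**Working it through.** **1. Order of events.** From Materials and Methods and the discontinuation list: end of surgery → envelope with assignment → emergency-room window → scheduled visit → PSQ-18 call 7–14 days later. The emergency-room rule therefore falls after allocation and before the primary outcome. The other item on the list, a surgical complication needing face-to-face care, may act before or after allocation depending on when the complication is recognised, so the point rests on the emergency-room item.

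**2. Possible bias.** Suppose a proportion p of an arm is removed and those patients would score g points below the patients who stay. The mean of everyone randomised to that arm is then the retained mean minus p × g, so the retained-only mean is too high by p × g. With the same g in both arms,

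shift = (difference in proportion removed) × g.

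The documents give neither quantity. As an assumed illustration, take two more removals in one arm of 32 and g = 20 (one SD): 2/32 × 20 = 0.0625 × 20 = 1.25 points, in favour of the arm with more removals. With equal removal and equal scores across arms the shift is 0.

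**3. Reproducing 64.** Inputs from Sample size: difference 20% of 70 = 14 points; SD 20; two-sided alpha 0.05; power 80%. The plan names no formula. The normal approximation gives

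n per arm = 2 × (1.960 + 0.842)² × 20² / 14² = 32.04, or 64.1 in total.

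This matches 64 (rounding each arm up strictly would give 66). Power at 32 per arm: 14 / (20 × √(2/32)) = 2.80; 2.80 − 1.96 = 0.84; power 79.96%. By t-test it is 78.7%. The inputs use up all 64, so no allowance for loss is contained in it.

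**4. If 64 is the number randomised.** Loss rates are assumed. Analysed: 64 × 0.95 = 60.8 → 61; 64 × 0.90 = 57.6 → 58; 64 × 0.80 = 51.2 → 51.

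| Assumed loss | Analysed | Power, normal | Power, t-test | Difference detectable with 80% power (normal) |
|---|---|---|---|---|
| 0% | 64 | 79.96% | 78.7% | 14.0 |
| 5% | 61 (30 + 31) | 78.0% | 76.7% | 14.35 |
| 10% | 58 (29 + 29) | 76.0% | 74.5% | 14.7 |
| 20% | 51 (25 + 26) | 70.5% | 68.8% | 15.7 |

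**5. If 64 is the number analysed,** the first row applies and power is essentially as stated.

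**The case against.** The plan says only that such a patient is ineligible to continue. A reader might infer that the protocol states her exclusion from the satisfaction analysis, but no sentence says this or says that she is not called. That stands, and it is why the point is worded as what the rule appears to do. The inference is still strong: the only planned PSQ-18 call follows the visit, and nothing provides for analysing her by assigned arm.

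A reader might also infer that the result will be biased, perhaps towards telemedicine. The documents do not support that. The emergency-room visit comes before the postoperative visit, so the visit format has not yet been delivered, and knowledge of the assignment is the only systematic route to unequal removal. Safety Procedures expects no significant difference in complications. Against this, the same section would halt the study if emergency-room visits rose by more than 10% in the experimental arm, so the plan itself allows that the arms might differ. The expectation of no difference does not protect the comparison. Bias is possible; it is not shown.

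Finally, a reader might infer that the trial is underpowered. That requires 64 to mean randomised, and the larger shortfalls require loss rates that the documents do not give. At 5% loss the fall is about two percentage points, which is small beside the uncertainty in a planning SD of 20 in what the Background calls a pilot. Taken alone, this half is a labelling point.

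**Conclusion.** The point holds as an analysis-population gap, with a lesser sample-size point attached. Read as written, the rule appears to remove randomised patients who know their arm from the primary comparison, and nothing elsewhere in the plan repairs this. The direction and size of any bias cannot be determined from the documents. The 1.25-point figure rests on two assumed inputs and only shows the scale.

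On sample size, 64 is the complete-data figure. If it is the number randomised, any loss takes power below the stated 80%: modestly at 5–10%, to about 70% at 20%, all assumed rates. If it is the number analysed, there is no shortfall beyond the choice of formula. Severity is moderate: the plan should be changed, but nothing here shows that its result would be wrong.

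**What to change.** 1. State that patients who meet a removal trigger after allocation stay in follow-up, with no change to how their care is delivered. Make the PSQ-18 call 7–14 days after whatever postoperative visit they have, about that visit, and include them in the primary analysis by assigned arm. If no visit takes place, count the score as missing in the assigned arm. Report missing scores by arm, including those from patients who cannot be reached by phone, since retention does not recover these.

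2. Label 64 as randomised or analysed. If it is the number randomised, restate the power or the detectable difference for the expected number analysed, using one named formula throughout.

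The cost is wording, a few extra calls, and tracking which visit each of these patients had. Some patients will be analysed in an arm whose visit type they did not receive, which can dilute the difference, and the stated power may look slightly less favourable. No extra patients are required. If the sponsor prefers to keep 64 analysed, the number randomised would be 64/0.95 → 68 at 5% loss or 64/0.90 → 72 at 10%. At the four patients per week given under Timeline, that is one or two more weeks. This would restore power but would not remove the selection problem, so it does not replace the first change.

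### The ED-visit comparison, followed as written, omits early post-randomisation events, and the halting rule gives no size for a complication increase and no scale for the ER 10%

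*Combined protocol and SAP*

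**What the plan says.** All references are to the combined protocol and SAP.

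- **Allocation (Materials and Methods).** "After surgical stop-time, patients will be allocated to either a traditional postoperative visit group" or to telemedicine. The envelope tells the patient her arm and how to "schedule the post-operative visit within a window between one and three weeks from the surgery".
- **Withdrawal after recruitment (list following the exclusion criteria).** A patient becomes ineligible to continue if the "participant visits the emergency room (ER) for postoperative complaints between surgery and scheduled postoperative visit".
- **Record review (Materials and Methods).** Charts are searched for "visits to the emergency department following the postoperative encounter (within the first 30 days after surgery").
- **Objective 3.** The arms are to be compared on surgery-related ED visits and delayed complications. Nothing restricts this to the period after the postoperative visit.
- **Monitoring (Safety Procedures).** "Interval analysis will be performed for every 20 patients recruited". The study stops if telemedicine shows an "increase of greater than 10% in visits to the emergency-room" for postoperative complaints, "or an increase in unexpected complications (wound infection, wound dehiscence, etc.), the study will be halted". The same paragraph expects no harm: "so we do not expect any significant difference regarding complications".

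**The concern.** There are two linked problems.

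**Ascertainment.** A pre-visit ER event happens after randomisation, in a patient who knows her arm. The withdrawal list removes her, and the chart review starts only at the visit. The ED comparison is then made in a group selected after randomisation. Its counting window opens on a day that varies by patient and could vary by arm. Objective 3 and the ER trigger are worded without this restriction, so the sections do not describe the same quantity.

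**Trigger wording.** The ER clause has a number but no scale (percentage points or relative change) and no window. The complication clause has no number at all. Two monitors holding the same table, say one wound infection against none, could reach opposite decisions. It is also unclear whether halting means a pause or termination. The plan itself expects no difference in complications, so how the rule behaves in that case matters.

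**Working it through.** **Plan's own figure.** The only computed figure is the sample size. Inputs from the Sample size section: difference 0.20 × 70 = 14, SD 20, two-sided alpha 0.05, power 80%. Total = 2 × 2 × [20 × (1.960 + 0.842) / 14]² ≈ 64.07, which reproduces 64. It is not in dispute.

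**Coverage of the ED review.** The visit falls on day 7 to day 21 and the review ends on day 30. Days covered: 30 − 7 = 23 down to 30 − 21 = 9. Days not searched: the first 7 to 21. Two patients with visits on days 7 and 14 are observed for 23 and 16 days, so a difference in visit timing between arms becomes a difference in exposure.

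**Looks.** Every 20 of 64 recruits gives looks at 20, 40 and 60, about 10, 20 and 30 per arm under 1:1 allocation.

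**Complication clause, read literally.** Halt if the telemedicine count exceeds the office count. At the first look with equal true rates, P(halt) = (1 − P(tie)) / 2. At an assumed 5% rate P(tie) = 0.463, so P(halt) = 0.268; at 1% P(tie) = 0.826, so P(halt) = 0.087. Carrying the cumulative binomial counts exactly through all three looks, with complete data at each:

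| Assumed rate, both arms | Literal clause | If 10 points also applied to complications |
|---|---|---|
| 0.5% | 13% | 0.1% |
| 1% | 22% | 0.4% |
| 3% | 41% | 3% |
| 5% | 49% | 8% |

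The last column needs an excess d with d/n > 0.10, that is 2, 3 and 4 events at n = 10, 20 and 30 per arm.

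**Allowing for accrual.** Looks are triggered by recruitment, and the Timeline section expects 4 recruits per week. At look 1 few patients have 30 days of follow-up. With events assumed even over 30 days, and surgery either on the day of recruitment or 14 days later (assumed), the literal clause halts about 17–19% of no-harm trials at a 1% rate and 42–46% at 5%.

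**ER clause at an assumed 5% rate, equal arms, full data.**
- Percentage points: 7.6%.
- Relative: (c + 1)/c > 1.10 whenever the office count c is below 10, so any excess triggers, giving 49%. If an office count of zero cannot trigger, 24%.

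**Cost of loosening the complication clause.** Under assumed true harm of 3% vs 10%, detection is 85% as written and 35% with a 10-point threshold. For 1% vs 5% it is 72% and 12%.

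**Effect of counting pre-visit ER events.** Take a 5% ER rate spread evenly over 30 days. With visits on day 7, 14 or 21, the post-visit rate is 5% × 23/30, 16/30 or 9/30. False ER triggers on the points reading are 5%, 3% and 1%, against 8% with all events. On the relative reading they are 45%, 39% and 29%, against 49%.

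**Power, only if halting means termination.** Two-sample t-test, difference 14, SD 20, every recruit completing the outcome: 32% at 10 per arm, 58% at 20, 76% at 30, against 79% at 32.

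**The case against.** The best defence has four parts.

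1. **Staff would know of early ER visits.** They must learn of a visit to apply the withdrawal criterion, and Safety Procedures does not exclude it. This stands. A reader might infer that these events never reach the safety monitor, but the documents do not say so: the chart review describes outcome collection, not the monitor's data source. What remains is that the sections are not tied together and that the ED comparison, followed as written, omits these events.
2. **A visit cannot cause events before it, and the objectives speak of delayed or unrecognised problems.** This is a fair reason to show post-visit events separately. It does not justify dropping the others, because patients know their arm from surgery onwards and their behaviour may differ before the visit.
3. **This is a small pilot, and a hair-trigger rule is cautious.** That is legitimate, and the detection figures show that a looser threshold loses much sensitivity. The plan does not say that this caution is intended. A reader could also carry the 10% over to complications, or take the wording to imply a test, but the text supports neither.
4. **All event rates are assumed.** True; hence the range shown.

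Two further inferences should be resisted. Full-data figures might suggest that most false halts come at the first look. Under the stated accrual, first halts at looks 1/2/3 are about 5/8/7% at a 1% rate and 18/18/10% at 5%, so that does not hold. Nor do the power figures show a certain loss: they apply only if halting means termination, and a safety stop is not normally judged by power for satisfaction.

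**Conclusion.** The concern holds in two parts and should be fixed.

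The firmer part is ascertainment, which rests on the text alone. Early ER events are post-randomisation, lead to withdrawal, and fall outside a review covering 9 to 23 of 30 days, while objective 3 and the ER trigger have no such limit.

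The second part is the undefined trigger. Read literally, one extra telemedicine complication halts a no-harm trial with probability about 22% at a 1% rate and 49% at 5% with full data, or about 17–19% and 42–46% under planned accrual. At a 5% ER rate, the missing scale alone moves the false-halt chance from about 8% to as much as 49%. These figures assume an exact 1:1 split, event rates that the documents do not give and, for the accrual version, even event timing. They describe one clause at a time. They do not show that the literal rule is wrong, only that its meaning and consequences are unstated.

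**What to change.** **Main change.** Record ER visits and complications from randomisation to day 30 in all randomised patients, including those who become ineligible to continue. Use this full count for objective 3 and give it to the safety monitor, tabulated by arm before and after the postoperative visit. At each look, show the numbers randomised and followed in each arm.

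**Wording.** Reconcile the two clauses in Safety Procedures: the scale of the 10%, what size of complication increase counts, and whether halting is a pause or termination. The sponsor should choose these values. If the literal rule is deliberately cautious, say so.

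**Cost.** Slightly more chart review and one table per look; no extra patients. If pre-visit events count towards the ER trigger, false triggers rise somewhat (points reading at an assumed 5% rate: from 1–5% to 8%), which is why the before/after split is useful. Any looser complication criterion would reduce sensitivity to harm, so that trade-off should be made openly.
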